Annex 4: Vas Scale

1. Postoperative Incisional Pain

[figure not shown]

Score 0 means no pain;

Score 10 means unbearable: severely affects sleep with other symptoms, or passive position;

2. Intraoperative suture performance indicators

Survey to be completed for the second case using ██████ and ██████ for each Investigator.

- Ease to pass through tissues

Score 0 means very easy to pass through tissues;

Score 5 means very difficult to pass through tissues;

- Surgical operation profile (including surgical “handfeel”)

Score 0 means the best “handfeel”;

Score 5 means the worst “handfeel”;

- Suture memory

Score 0 means no suture memory;

Score 5 means the suture memory is very serious;

- Wear resistance of suture

Score 0 means the wear resistance is very good;

Score 5 means the wear resistance is very bad.

Health Questionnaire

Simplified Chinese Version for China

(Simplified Chinese version for China)

China (Simplified Chinese) © 2011 EuroQol Group EQ-5D™ is a trade mark of the EuroQol Group

Under each heading, please tick the ONE box that best describes your health today

MOBILITY

- I have no problems in walking about ☐
- I have slight problems in walking about ☐
- I have moderate problems in walking about ☐
- I have severe problems in walking about ☐
- I am unable to walk about ☐

SELF-CARE

- I have no problems washing or dressing myself ☐
- I have slight problems washing or dressing myself ☐
- I have moderate problems washing or dressing myself ☐
- I have severe problems washing or dressing myself ☐
- I am unable to wash or dress myself ☐

USUAL ACTIVITIES (e.g. work, study, housework, family or leisure activities)

- I have no problems doing my usual activities ☐
- I have slight problems doing my usual activities ☐
- I have moderate problems doing my usual activities ☐
- I have severe problems doing my usual activities ☐
- I am unable to do my usual activities ☐

PAIN/DISCOMFORT

- I have no pain or discomfort ☐
- I have slight pain or discomfort ☐
- I have moderate pain or discomfort ☐
- I have severe pain or discomfort ☐
- I have extreme pain or discomfort ☐

[figure not shown]
ANXIETY/DEPRESSION

- I am not anxious or depressed ☐
- I am slightly anxious or depressed ☐
- I am moderately anxious or depressed ☐
- I am severely anxious or depressed ☐
- I am extremely anxious or depressed ☐

- We would like to know how good or bad your health is TODAY.
- This scale is numbered from 0 to 100.
- 100 means the best health you can imagine.
0 means the worst health you can imagine.
- Mark an X on the scale to indicate how your health is TODAY.
- Now, please write the number you marked on the scale in the box below.

YOUR HEALTH TODAY =

The best health you
can imagine

The worst health
you can imagine

Incision Characteristics	Proportion of Wound Affected					
	0	<20	20-39	40-59	60-79	>80
Serous exudate	0	1	2	3	4	5
Erythema	0	1	2	3	4	5
Purulent exudate	0	2	4	6	8	10
Separation of deep tissues	0	2	4	6	8	10
Points are scored for daily wound inspection.						
Additional Treatment			Points			
Antibiotics			10			
Drainage of pus under local anesthesia			5			
Debridement of wound (general anesthesia)			10			
Serous discharge*			Daily 0-5			
Erythema*			Daily 0-5			
Purulent exudate*			Daily 0-10			
Separation of deep issues*			Daily 0-10			
Isolation of bacteria			10			
Stay as inpatient prolonged over 14 days			5			
* Given score only on five of seven days. Highest weekly score used.						
Category of Infection						
Total Score**			Definition			
0-10			Satisfactory healing			
11-20			Disturbance of healing			
21-30			Minor wound infection			
31-40			Moderate wound infection			
>40			Severe wound infection			
** When calculating the total score, scores of independent incision characteristics and additional treatments should be added.

## MODIFICATION HISTORY

UNIQUE IDENTIFIER FOR THIS VERSION	DATE OF THE DOCUMENT VERSION	AUTHOR	SIGNIFICANT CHANGES FROM PREVIOUS AUTHORIZED VERSION
1.1	2020-07-23	[name]	NOTAPPLICABLE

## 1. INTRODUCTION

This document describes the rules and conventions to be used in the presentation and analysis of efficacy and safety data for Protocol ESC-201702. It describes the data to be summarized and analyzed, including specifics of statistical analyses to be performed.

This statistical analysis plan (SAP) is based on protocol version 2.0, dated 30/Sep/2019.

## 2. STUDY OBJECTIVES

The primary objective of this study is to evaluate the efficacy and safety of two types of absorbable surgical sutures - [REDACTED] Knotless Plus Tissue Control Device and [REDACTED] Knotless Tissue Control Device (hereinafter referred to as [REDACTED] and [REDACTED]) used in thyroid surgery to suture surgical incision.

For the primary efficacy endpoint, the study aims to demonstrate the non-inferiority of each of the two types of absorbable surgical sutures to the control group with respect to achieving Grade A healing of surgical incision(success).

## 3. STUDY DESIGN

This is a three-arm prospective, multi-center, randomized controlled study comparing the efficacy (non-inferiority tests) and safety of [REDACTED] and [REDACTED] to the control group [REDACTED] with [REDACTED] in soft tissue suturing in subjects who undergo thyroid surgery.

In China, a total of approximately 501 subjects undergoing thyroid surgery in approximately 10 study sites will be enrolled into the study. Each site should enroll no more than 125 subjects (25% of the total number).

Prior to surgery, subjects will be randomized to the investigational group 1 ([REDACTED]), investigational group 2 ([REDACTED]) or the control group according to the allocation ratio of 1:1:1 using central randomization. The primary efficacy endpoint is the proportion of subjects achieving Grade A wound healing (success) of surgical incision in each group. A blind assessment will be performed on the wound healing status by independent Central Imaging evaluators on Day 5-7 post-surgery using the imaging data (a picture of complete neck anterior view, covering full length of the incision).

The subjects will be followed up on Day 5-7 and Day 28-35 post-surgery.

A schedule of study activities is included in section 7.2.1 of the study protocol. In addition, the study procedures and evaluations performed at each visit are included in section 7.2.3 of the protocol.

## 4. PLANNED ANALYSES

## 5. ANALYSIS SETS

Agreement and authorization of subjects included/excluded from each analysis set will be conducted prior to the unblinding of the study.

## 5.1. FULL ANALYSIS SET (FAS)

FAS consists of all the enrolled subjects who were randomized and at least post-baseline effectiveness endpoint evaluation.

## 5.2. PER PROTOCOL SET (PP)

PP (evaluable) Set contains all the subjects in the FAS who have no major protocol deviation, have data available for primary efficacy endpoint and do not meet any of the following criteria:

o Subject undergoes any of the following procedures, in addition to thyroidectomy:

- 1、 Any surgical procedure which require additional neck incisions or extend the original incision;
- 2、 Cervical lymph node dissection (except the dissection of lymph nodes in the VI area);
- 3、 Other unplanned surgical procedures (except the procedure that the investigator doesn't think it will affect the original incision's healing)

- o Subject's intraoperative frozen pathology or postoperative paraffin section pathology suggests anaplastic thyroid cancer;
- o Subject receives any surgical procedures that lead to re-opening of the cervical incision during the period from the wound closure to the completion of study, except for surgeries related to surgical incision complication or study device.

## 5.3. SAFETY SET

Safety Set contains all the enrolled subjects who receive surgery, product use, and at least post-baseline follow up

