7.2.3 Study Procedures

1) Visit 1 – Screening/ Baseline visit

The following screening procedures should be completed prior to any study procedure:

- The subject must be given enough time to review and sign the ICF;

- Collection of demographic information (e.g. date of birth, gender, ethnic origin, etc.);
- Review and collection of medical/surgical history;
- Urine/blood pregnancy test: The result of the examination completed within 7 days prior to the signing of ICF is acceptable. If multiple examinations are completed, the result of the examination closest to the time of operation shall prevail;
- Fasting plasma glucose test: The result of the examination completed within 7 days prior to the signing of ICF is acceptable. If multiple examinations are completed, the result of the examination closest to the time of operation shall prevail;
- Review/collection of inclusion/exclusion criteria, and determining whether the subject meets the criteria or not;
- Physical examination: Including body height, body weight, physical examination results of the head and neck, and other contents;
- Concomitant medications: Medications started within 7 days prior to the signing of ICF or currently used
- EQ-5D-5L。

a. Screening

Subjects will be consented prior to any study-specific screening procedures being conducted. Subjects will be considered enrolled into the study upon satisfaction of the following criteria:

- Completion of the informed consent process;
- It is determined by the investigator that the subject meets all inclusion criteria and does not meet any exclusion criteria (Section 7.1.5). The verification must be conducted by the Principal Investigator (PI) and/or authorized investigators prior to randomization.

b. Screen Failures

Subjects who signed the ICF and were screened but not successfully randomized will be considered screen failures. For subjects who are determined to be screen failures, only the following data will be collected:

- Informed consent date;
- Demographic information (age, race, gender, and ethnicity);
- Reason for screening failure.

2) Visit 2 -Randomization

The following information must be obtained during randomization:

- Confirmation of inclusion / exclusion criteria;
- Update of medical/surgical history (prior to randomization);
- Randomization: Central randomization prior to the surgical procedure;
- Concomitant medications;
- Adverse event (AE) (collected since randomization).

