the two group comparisons, the p-value associated with the non-inferiority test will be calculated using the Normal approximation Z (pooled) statistic. If the smaller p-value is smaller than 0.0125, then the null hypothesis associated with this p-value will be rejected and it will be concluded that the associated Test product is non-inferior to Control; subsequently, the larger p-value will be compared to 0.025 in order to test the non-inferiority of the other Test product to Control. If the smaller p-value is larger than 0.0125, then neither of the null hypotheses can be rejected and it will be concluded that, for both investigational devices, the study failed to demonstrate non-inferiority to Control.

The primary endpoint will be analyzed using the Full Analysis Set (FAS) and Per-Protocol (PP) sets. The PP analysis will be considered the primary analysis, while the FAS analysis will be considered supportive. The analysis sets for this study are defined in section 8.8.

The following **secondary efficacy endpoints** will be summarized descriptively by treatment group for the FAS:

1. Incision suturing time, defined as the time required from the first needle insertion for stitching ribbon muscles to the completion of intradermal suture (min);
2. Modified Hollander Wound Evaluation Scale;
3. Postoperative incision pain score (VAS Scale);
4. Health related quality of life scale (EQ-5D-5L).

In addition, the following safety endpoints will be summarized descriptively t by treatment group for the Safety analysis set:

1. Incidence of postoperative SSI;
2. ASEPIS score (only assessed in subjects with confirmed SSI);
3. Incidence of incisional wound separation or wound dehiscence requiring intervention;
4. Incidence of delayed incisional wound healing events;
5. Incidence of other AEs;
6. Product complaints.

The incidence of AEs will be assessed according to the classification of event and summarized descriptively by treatment groups. Incidence of AEs will also be assessed by onset time (intraoperative or postoperative), relationship to study surgical procedure, relationship to the study product, severity, and seriousness.

All continuous variables will be summarized by number of subjects, mean, standard deviation, median, minimum and maximum. All categorical data will be summarized by frequencies and associated percentages. No inferential statistics will be generated for secondary efficacy and safety endpoints.

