8.8 Selection Criteria and Reason of Subjects Included in the Analysis

All subjects that meet the inclusion/exclusion criteria are considered to meet the requirements for recruitment.

Three analysis sets in the study are defined for this study, as follows:

- FAS consists of all the enrolled subjects who were randomized and for whom the randomized suture materials were used for incision closure.
- PP (evaluable) Set contains all the subjects in the FAS who have no major protocol

deviation, have data available for primary efficacy endpoint and do not meet any of the following criteria:

- Subject undergoes any of the following procedures, in addition to thyroidectomy:
 - 1、 Any surgical procedure which require additional neck incisions or extend the original incision;
 - 2、 Cervical lymph node dissection (except the dissection of lymph nodes in the VI area);
 - 3、 Other unplanned surgical procedures (except the procedure that the investigator doesn't think it will affect the original incision's healing)
- Subject's intraoperative frozen pathology or postoperative paraffin section pathology suggests anaplastic thyroid cancer;
- Subject receives any surgical procedures that lead to re-opening of the cervical incision during the period from the wound closure to the completion of study, except for surgeries related to surgical incision complication or study device.
- Safety Set contains all the enrolled subjects who receive surgery.

Major protocol deviations are deviations that have an impact on the primary endpoint assessment or randomization. These will be determined prior to database lock.

The analysis of primary efficacy endpoint will be performed using FAS and PP Sets. However, while the primary analysis is based on the PP Set, FAS analysis will only be used as supplemental analysis.

The secondary efficacy endpoints will be analyzed using the FAS, while the safety endpoints will be analyzed using the Safety Set.

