## **14. SAFETY ENDPOINTS**

All outputs for safety endpoints will be based on the Safety Analysis Set.

Incidence of postoperative SSI、ASEPSIS score (only assessed in subjects with confirmed SSI)、Incidence of incisional wound separation or wound dehiscence requiring intervention、Incidence of delayed incisional wound healing events、Incidence of other AEs、and Product complaints will be summarized descriptively by treatment group and overall.

There will be no statistical comparisons between the treatment groups for safety data, unless otherwise specified with the relevant section.

The incidence of AEs will be assessed according to the classification of event and summarized descriptively by treatment groups. Incidence of AEs will also be assessed by onset time (intraoperative or postoperative), relationship to study surgical procedure, relationship to the study device, severity, and seriousness.

The specific safety endpoint incidences and other adverse events will be summarized descriptively in each treatment group and overall by presenting the number and percentage of subjects experiencing the occurrence of each event.

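### SAP 5.3 narrows the protocol's Safety Set with a product-use condition and an undefined follow-up condition, so some operated subjects can be left out of the safety summary tables

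*SAP*

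**What the plan says.** Protocol 8.8 defines the set by a single event: "Safety Set contains all the enrolled subjects who receive surgery". It adds that the secondary endpoints use the FAS, "while the safety endpoints will be analyzed using the Safety Set".

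SAP 5.3 is narrower: "Safety Set contains all the enrolled subjects who receive surgery, product use, and at least post-baseline follow up". No visit, contact or minimum amount of follow-up is named. SAP 1 states the basis of the plan: "This statistical analysis plan (SAP) is based on protocol version 2.0, dated 30/Sep/2019". That is the current protocol version, and the SAP does not list or explain a departure from it. SAP 14 then says: "All outputs for safety endpoints will be based on the Safety Analysis Set". No other set is defined under that name, so it is taken to be the set in SAP 5.3. SAP 3 describes follow-up in one sentence: "The subjects will be followed up on Day 5-7 and Day 28-35 post-surgery".

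**The concern.** Two documents that should agree define the same analysis set differently, and the later one is more restrictive. Both added conditions can remove people who had the operation.

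- **Follow-up.** Some safety information arises at the operation itself or soon after it. A subject who has an intra-operative event and then dies, withdraws or is lost before the Day 5-7 visit would be counted under the protocol, but perhaps not under the SAP. Protocol 7.1.5 also says that subjects who leave early stay in the analysis of results.
- **Product use.** An operated subject in whom no study suture was used is in the protocol's set and outside the SAP's. The protocol nevertheless arranges a withdraw visit to collect adverse events and product complaints from randomized subjects without study sutures.

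Safety is part of the primary objective and is reported only descriptively, so the counts and percentages in these tables are the safety evidence. No imputation is planned (SAP 7.1) that would offset an exclusion.

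**Working it through.** **1. The definitions side by side**

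| Condition | Protocol 8.8 | SAP 5.3 |
|---|---|---|
| Enrolled | required | required |
| Had surgery | required | required |
| Product used | not required | required |
| Post-baseline follow-up | not required | required; visit and amount not stated |

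**2. Safety data that exist before Day 5-7**

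- Protocol 7.2.3 starts adverse event collection at randomization (Visit 2) and records adverse events and product complaints at surgery (Visit 3).
- Protocol 8.1 and SAP 14 plan adverse event incidence by intra-operative or post-operative onset. SAP 14.1.3 plans a summary of fatal events.
- These summaries therefore rest partly on data that do not need a Day 5-7 visit.

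**3. The denominator used for illustration**

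The plan's figures (Protocol 8.2.1, SAP 13.1.1) are 150 evaluable and 167 enrolled per arm. With success 0.98 in both arms, margin 0.05, one-sided alpha 0.0125 and 80% power:

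- n = (z for 0.0125 + z for 0.80 power)² × 2 × 0.98 × 0.02 / 0.05² = (2.241 + 0.842)² × 0.0392 / 0.0025 = 149.04, rounded up to 150. Power at 150 is 80.3% by this approximation.
- 150 / (1 − 0.10) = 166.7, rounded up to 167; 3 × 167 = 501.

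This point does not dispute those figures. They only supply the arm size of 167.

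**4. Effect of an exclusion on a rate**

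Let n be the subjects operated on in an arm, e those with an event, m those excluded by SAP 5.3, and k the excluded subjects who had the event.

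- Protocol rate = e / n
- SAP rate = (e − k) / (n − m)
- The SAP rate is the lower of the two only if k/m exceeds e/n, that is, only if the excluded subjects have events more often than the arm as a whole.

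Take n = 167, all operated on with the study suture. The values of e, k and m are assumptions; the documents give none.

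| e | m | k | Protocol | SAP |
|---|---|---|---|---|
| 1 | 1 | 1 | 1/167 = 0.60% | 0/166 = 0.00% |
| 2 | 1 | 1 | 2/167 = 1.20% | 1/166 = 0.60% |
| 3 | 2 | 2 | 3/167 = 1.80% | 1/165 = 0.61% |
| 5 | 2 | 2 | 5/167 = 2.99% | 3/165 = 1.82% |
| 3 | 17 | 0 | 3/167 = 1.80% | 3/150 = 2.00% |

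If nobody is excluded, the two rates are equal. The last row shows the opposite direction: leaving out event-free subjects raises the rate.

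**5. How many could be affected**

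The only loss figure is the 10% total dropout: 0.10 × 167 = 16.7 per arm, or about 50 over three arms. A subject lost between Day 5-7 and Day 28-35 already has follow-up and stays in the set, so 16.7 is a ceiling for loss before Day 5-7, not an estimate of it. The documents give no figure for subjects operated on without a study suture.

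**The case against.** A reader might infer that every operated subject without a Day 5-7 visit certainly disappears from all safety rates. The documents do not settle that. Protocol 7.1.7 calls Visits 2 to 5 follow-up visits, which would include the surgery visit, and on that wording a subject with an intra-operative event stays in. SAP 3, with follow-up only at Day 5-7 and Day 28-35, points the other way. Exclusion is the likelier reading but not a certain one.

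A reader might also infer that complication rates are biased downward in general. That requires excluded subjects to have more events than retained ones, which is plausible for intra-operative events, complaints and early deaths but is not shown. Surgical site infection and dehiscence are poor examples. Protocol 7.2.1 schedules their assessment only at the two post-operative visits, so a subject with neither visit will usually have no recorded case to lose.

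Nor are events hidden. SAP 14.1 puts all adverse events in the listings, SAP 14.2 lists device defects, and SAP 9 reports disposition and the number in each analysis set. Protocol 7.1.5 and 14.5 also require adverse events to be followed after they occur, so a living subject with an event and no post-operative follow-up of any kind should be uncommon. Death before Day 5-7 is the clearest exposed case.

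All of this limits the size of the problem. None of it explains why the SAP departs from the protocol, and the unclear follow-up term leaves inclusion open to interpretation. The product-use condition is untouched by these arguments, apart from the listings and disposition tables.

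**Conclusion.** The concern holds as a conflict between the two definitions, with a possible effect on the summary tables. As written, SAP 5.3 can remove two kinds of operated subject from numerator and denominator: those with an intra-operative adverse event, a product complaint or an early death and no later visit, and those in whom no study suture was used. The first group depends on reading follow-up as the Day 5-7 and Day 28-35 visits; the second does not.

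The number of subjects is unknown and probably small. Each excluded subject with an event takes one off the arm's count, about 0.6 percentage points in an arm of 167. That matters mainly for rare events, where a single case can be the whole count. Safety is not tested, so no hypothesis test or success criterion is affected. The change is worth making because the set underlies every safety summary and the correction is simple.

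**What to change.** Before database lock, replace the text of SAP 5.3 with the protocol 8.8 definition: "Safety Set contains all the enrolled subjects who receive surgery". Both added conditions should go. Deleting only the follow-up condition would leave product use in place, and redefining the set by use of a study suture would still depart from the protocol. An analysis by suture actually received is specified in neither document and is not needed to resolve this point.

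The cost is one sentence of SAP text. Sample size, power, alpha and the primary analysis are unchanged, and no additional data collection is needed.
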